9.1.3 Assessment of Adverse Events by the Investigator

The Investigator will assess the severity (intensity) of each adverse event as mild, moderate, severe, life-threatening, or death and will also categorize each adverse event as to its potential relationship to study drug using the categories of related or not related.

Assessment of Severity

The severity of all adverse events should be graded according to the Common Terminology Criteria for Adverse Events (CTCAE) Version 5.0. For those adverse event terms not listed in the CTCAE, the following grading system should be used:

- CTCAE Grade 1: Mild; asymptomatic or mild symptoms; clinical or diagnostic observations only; intervention not indicated
- CTCAE Grade 2: Moderate; minimal local or noninvasive intervention indicated; limiting age-appropriate instrumental activities of daily living
- CTCAE Grade 3: Severe or medically significant but not immediately life-threatening; hospitalization or prolongation of hospitalization indicated; disabling; limiting self-care activities of daily living
- CTCAE Grade 4: Life-threatening consequences; urgent intervention indicated
- CTCAE Grade 5: Death related to the adverse event

Causality Assessment

The relationship of an adverse event to the administration of study drug is to be assessed according to the following definitions:

Not related (unrelated, not related, unlikely to be related) – The time course between the administration of study drug and the occurrence or worsening of the adverse event rules out a

causal relationship and another cause (concomitant drugs, therapies, complications, etc) is suspected.

Related (possibly, probably, or definitely related) – The time course between the administration of study drug and the occurrence or worsening of the adverse event is consistent with a causal relationship and no other cause (concomitant drugs, therapies, complications, etc) can be identified.

The definition implies a reasonable possibility of a causal relationship between the event and study drug. This means that there are facts (evidence) or arguments to suggest a causal relationship.

The following factors should also be considered:

- The temporal sequence from study drug administration-

The event should occur after study drug is given. The length of time from study drug exposure to the event should be evaluated in the clinical context of the event.

- Underlying, concomitant, intercurrent diseases-

Each report should be evaluated in the context of the natural history and course of the disease being treated and any other disease the patient may have.

- Concomitant medication-

The other drugs the patient is taking or the treatment the patient receives should be examined to determine whether any of them might be recognized to cause the event in question.

- The known response pattern for this class of study drug-

Clinical and/or preclinical data may indicate whether a particular response is likely to be a class effect.

- Exposure to physical and/or mental stresses-

The exposure to stress might induce adverse changes in the recipient and provide a logical and better explanation for the event.

- The pharmacology of study drug-

The known pharmacologic properties (absorption, distribution, metabolism, and excretion) of study drug should be considered.

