9.1.1 Adverse (Drug) Reaction

All noxious and unintended responses to a medicinal product related to any dose should be considered an ADR. “Responses” to a medicinal product means that a causal relationship between a medicinal product and an adverse event is at least a reasonable possibility, ie, the relationship cannot be ruled out.

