3.7.1 Adverse Events

AEs will be monitored and documented from the time informed consent is obtained until Week 28. All AEs will be coded using MedDRA v24.0.

Treatment-emergent AEs (TEAEs) are defined as AEs that start on or after the first dose of study drug.

Events of serious hypersensitivity that are Grade 3 or higher or lead to treatment study drug discontinuation and vacuolization associated with immunoglobulin will be monitored as AESIs.

An overview of AEs will be provided including counts and percentages of patients (and event counts) with the following:

- Any TEAEs
- Any Grade 3 or higher TEAEs
- Any study drug related TEAEs
- Any study drug related Grade 3 or higher TEAEs
- Any AEs related to anti-CMV rescue medication
- Any AESIs
- Any Grade 3 or higher AESIs
- Any SAEs
- Any treatment-emergent serious AEs (TESAEs)
- Any TEAEs leading to discontinuation of study drug
- Any TEAEs leading to discontinuation of study
- Any AEs leading to death
- Any AEs related to COVID-19

Numbers and percentages of patients will also be presented by SOC and PT for each category in the summary tables.

Listings will be presented for AEs, Grade 3 or higher AEs, SAEs and TEAEs leading to discontinuation of study drug.

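### The two causality categories in Protocol 9.1.3 leave some events unclassified and set a stricter test for Related than the ADR definition in 9.1.1

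*Protocol*

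**What the plan says.** Protocol 9.1.3 has the investigator judge each adverse event "using the categories of related or not related". There is no third option.

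- *Not related* is headed "Not related (unrelated, not related, unlikely to be related" and has two conditions joined by 'and'. The first is that timing must exclude study drug as the cause. The second is in the closing words of the definition: "causal relationship and another cause (concomitant drugs, therapies, complications, etc) is suspected".
- *Related* is headed "Related (possibly, probably, or definitely related" and also has two conditions joined by 'and': the time course "is consistent with a causal relationship and no other cause (concomitant drugs, therapies, complications, etc) can be identified".

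The text right after these definitions says that they carry a reasonable-possibility standard. It then lists factors to weigh, including concomitant medication and underlying disease.

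Protocol 9.1.1 sets the threshold for an adverse drug reaction (ADR): "a causal relationship between a medicinal product and an adverse event is at least a reasonable possibility, ie, the relationship cannot be ruled out".

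The category is used in two places. SAP 3.7.1 tabulates "Any study drug related TEAEs" and the Grade 3 or higher subset, each also by system organ class and preferred term. Protocol 9.3 asks for serious events that come to light after the reporting window only if they are considered related.

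**The concern.** A two-way call should place every event in exactly one category, and the protocol should use one threshold for drug causality throughout. Section 9.1.3 does neither.

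The combination that falls between the categories is an ordinary one here. Patients receive their first dose within 7 days of a kidney transplant. The SAP baseline list (3.3.4) names nine immunosuppressive agents or classes and six induction agents, and patients who enter rescue also receive anti-CMV agents. For many adverse events an investigator will be able to name another possible cause alongside study drug.

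Safety is part of the primary objective. If one site follows the condition that no other cause can be found and another follows the *possibly related* label, the related-event rows mix two standards, and a reader of the study report cannot tell which one lies behind a given count.

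**Working it through.** The plan states no figure on this point, so the check is one of logic.

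**Step 1. Inputs.** Each definition in 9.1.3 uses two facts: whether the time course is compatible with study drug or rules it out, and whether another cause is present. That gives four combinations.

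**Step 2. Apply both definitions, then 9.1.1.**

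| Timing | Other cause | *Related*? | *Not related*? | Category under 9.1.3 | ADR under 9.1.1? |
|---|---|---|---|---|---|
| Rules out | Yes | No | Yes | Not related | No |
| Compatible | No | Yes | No | Related | Yes |
| Compatible | Yes | No (other cause) | No (timing) | **None** | **Yes** |
| Rules out | No | No (timing) | No (no other cause) | **None** | No |

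Two of the four combinations have no category. The third row is also a contradiction: the event fails *Related* in 9.1.3 but meets the ADR test in 9.1.1. The fourth row is a gap only.

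The protocol speaks of another cause being identified in one definition and suspected in the other. This does not change the result. Compatible timing alone defeats *Not related*, and an identifiable other cause alone defeats *Related*.

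**Step 3. Compare labels with definitions.** *Possibly related* sits under *Related*, although that definition allows no other identifiable cause. *Unlikely to be related* sits under *Not related*, although that definition needs timing that excludes causality; an unlikely relationship has not necessarily been excluded.

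**Step 4. An example from the protocol's own facts.** Suppose haemoglobin falls after a patient starts valganciclovir in the Rescue Phase.

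- The introduction (section 1) links ganciclovir and valganciclovir to bone marrow depression, so another cause can be named.
- The rationale (1.1) reports lower erythrocyte measures in 3 of 12 monkeys at 100 mg/kg and does not exclude an effect of NPC-21 on peripheral erythrocytes.
- It gives a half-life of 612.30 to 790.41 hours: 612.30 / 24 = 25.5 days and 790.41 / 24 = 32.9 days. Timing can therefore stay compatible for weeks after the last dose.

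This event falls in the third row.

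**Step 5. Size.** Let q be the share of time-compatible events for which another cause can be identified. Read literally, the share that misses *Related* is q and the share captured is 1 − q.

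| q (assumed) | Misses *Related* | Captured |
|---|---|---|
| 0.2 | 20% | 80% |
| 0.5 | 50% | 50% |
| 0.8 | 80% | 20% |

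The documents give no value for q, so this table shows sensitivity and is not an estimate.

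**The case against.** The strongest reply is that 9.1.3 does not have to be read mechanically. The sentence after the definitions restates the reasonable-possibility standard of 9.1.1, *possibly related* is listed under *Related*, and the listed factors call for judgement. An investigator can therefore choose *Related* for an event with a competing cause. This stands, and it limits the consequence. It does not remove the defect: the sentence comments on the definitions without withdrawing the no-other-cause condition, and the factors give no rule for two plausible causes.

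A reader might infer four stronger things that the documents do not support.

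- *Most plausible drug reactions cannot be classed as related.* 'Cannot' ignores the mitigating text, and 'most' needs q above 0.5, which no document shows. A list of co-medications does not say how often events have another cause.
- *The bias must be downward.* The literal text bars third-row events from *Not related* too, so they could go either way. Under-counting is possible but not established.
- *Expedited and serious-event reporting fail.* Serious events from consent to Week 28 are reported within 24 hours whatever the cause (9.3). Events of special interest are not defined by relatedness (9.1.4). The SUSAR definition (9.1.2) does not cite the 9.1.3 categories. The infusion-reaction trigger for considering stopping the study (4.3) uses grade and count.
- *The comparison between arms is biased.* The plan predicts primary events in 60% on placebo and 30% on 6 mg/kg by Week 16, so rescue drugs as a competing cause could differ by arm. But investigators judge under the blind with the same wording, and no figure links rescue to causality calls.

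It is also true that the main safety evidence, all-causality events by randomised arm, does not depend on relatedness.

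**Conclusion.** Wrong as written. The categories are not exhaustive (two of four combinations have no category), and the literal definition of *Related* is stricter than the ADR definition in 9.1.1 and than its own *possibly related* label. Both conclusions follow from the text and need no numerical assumption.

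The effect is narrower than the defect. What is exposed is the related and related Grade 3 or higher rows of SAP 3.7.1 with their breakdowns, and the reporting of related serious events after the window. The likely result is inconsistent classification with possible under-counting, of unknown size. That these patients often have competing causes is a judgement from the listed co-medication, not a documented rate. All-causality tables and serious-event reporting to Week 28 are not affected.

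**What to change.** Reconcile 9.1.1 and 9.1.3 to one threshold with two exhaustive categories, for example:

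- *Related*: a causal relationship is a reasonable possibility, ie, it cannot be ruled out, even if other causes are possible.
- *Not related*: all other events.

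The residual second category closes both gaps. State explicitly where *unlikely to be related* falls, because a cannot-be-ruled-out test could move it from *Not related* to *Related*. Carry the same wording into the eCRF completion guidance.

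The SAP addendum records database lock on 30 March 2023, and new wording does not change calls already recorded. For those, the study report should say which standard investigators applied, caveat the related-event rows, and rest the safety conclusions on the all-causality comparison by arm.

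The cost is definition text, eCRF guidance and a paragraph in the report; treatment and visits do not change. The downside is that the count of related events may rise where the new wording is used.

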9.1.4 Adverse Events of Special Interest

The Investigator will monitor each patient for clinical and laboratory evidence for predefined adverse events of special interest (AESIs) throughout the patient's participation in this study.

The Investigator will assess and record any additional information on the AESI in detail on an adverse event form, which must be submitted within 24 hours of awareness of the event.

Events of serious hypersensitivity that are Grade 3 or higher or lead to treatment discontinuation will be monitored as AESIs during this study.

During the course of the study, additional AESIs may be identified by the Sponsor.

Adverse events of special interest must be recorded in the eCRF.

9.2 Serious Adverse Events

An adverse event or adverse reaction is considered serious if, in the view of either the Investigator or Sponsor, it results in any of the following outcomes:

- Death.
- A life-threatening adverse event.

Note: The term “life-threatening” in the definition of “serious” refers to an event in which the patient was at risk of death at the time of the event; it does not refer to an event which hypothetically might have caused death if it were more severe.

- Requires hospitalization or prolongation of existing hospitalizations.

Note: Any hospitalization requiring admission for at least 1 day or an overnight stay will be considered an inpatient hospitalization. An emergency room or urgent care visit without hospital admission will not be recorded as an SAE under this criterion, nor will hospitalization for a procedure scheduled or planned before signing of informed consent, or elective treatment of a preexisting condition that did not worsen from Baseline. However, unexpected complications and/or prolongation of hospitalization that occur during elective surgery should be recorded as adverse events and assessed for seriousness. Admission to the hospital for social or situational reasons (ie, no place to stay, live too far away to come for hospital visits, respite care) will not be considered inpatient hospitalizations.

- A persistent or significant disability/incapacity or substantial disruption of the ability to conduct normal life functions.
- A congenital anomaly/birth defect.
- An important medical event.

Note: Important medical events that do not meet any of the above criteria may be considered an SAE when, based upon appropriate medical judgment, they may jeopardize the patient and may require medical or surgical intervention to prevent one of the outcomes listed above. Examples of such medical events include allergic bronchospasm requiring intensive treatment in an emergency room or at home, blood dyscrasias or convulsions that do not result in inpatient hospitalizations, or the development of drug dependency.

9.3 Serious Adverse Event Reporting – Procedures for Investigators

Initial Reports

All SAEs occurring from the time informed consent is obtained until Week 28 must be reported to [REDACTED] within 24 hours of the knowledge of the occurrence. Should the patient terminate the study early, SAEs should be reported up until the Early Termination visit or 90 days after the last administration of study drug, whichever is later. After the reporting window, any SAE that the Investigator becomes aware of and is considered related to study drug should be reported to [REDACTED] or the Sponsor/designee.

To report the SAE, complete the SAE form electronically in the electronic data capture (EDC) system for the study. When the form is completed, [REDACTED] will be notified electronically by the EDC system and will retrieve the form. If the event meets serious criteria and it is not possible to access the EDC system, send an email to [REDACTED] at [REDACTED]

[REDACTED] or call [REDACTED] (phone number listed below), and fax/email the completed paper SAE form to [REDACTED] (contact information listed in Section 9.6) within 24 hours of awareness. When the EDC system becomes available, the SAE information must be entered within 24 hours of the system becoming available.

All SAEs must be followed with appropriate medical management until resolved or stabilized.

The site Investigator is responsible for promptly notifying the Institutional Review Board (IRB)/Independent Ethics Committee (IEC) or equivalent in accordance with local regulations of all SAEs.

Follow-Up Reports

The Investigator must continue to follow the patient until the SAE has subsided or until the condition becomes chronic in nature, stabilizes (in the case of persistent impairment), or the patient dies.

Clinically significant laboratory abnormalities will be followed up until they have returned to normal, or a satisfactory explanation has been provided. Additional information (including but not limited to laboratory results) relative to the subsequent course of such an abnormality noted for any patient must be made available to the study monitor.

New or updated information will be recorded in the EDC system. For the purpose of reporting, significant follow-up information corresponds to new medical or administrative information that could impact the assessment or management of a case or could change its seriousness criteria.

Within 24 hours of receipt of follow-up information, the Investigator must update the SAE form electronically in the EDC system for the study and submit any supporting documentation (eg, patient discharge summary or autopsy reports) to [REDACTED] via fax or email. If it is not possible to access the EDC system, refer to the procedures outlined above for the initial reporting of SAEs.

9.4 Pregnancy Reporting

If a patient becomes pregnant during the study following administration of study drug or within 90 days following the last dose, the Investigator is to stop dosing with study drug immediately and the patient should be withdrawn from the study. Early termination procedures should be implemented at that time.

Pregnancy is not considered to be an adverse event or SAE; however, it must be reported to [REDACTED] within 24 hours of knowledge of the pregnancy.

[REDACTED] will then provide the Investigator/site the Exposure In Utero (EIU) form for completion. The Investigator/site must complete the EIU form and fax/email it back to [REDACTED].

If the female partner of a male patient becomes pregnant while the patient is receiving study drug or within 90 days following the last dose, the Investigator should notify [REDACTED] as described above and obtain informed consent for the collection of information regarding the pregnancy.

The pregnancy should be followed until the outcome of the pregnancy, whenever possible. Once the outcome of the pregnancy is known, the EIU form should be completed and faxed/mailed to [REDACTED]. If the outcome of the pregnancy meets the criteria for immediate

classification as an SAE (ie, postpartum complication, spontaneous abortion, stillbirth, neonatal death, or congenital anomaly), the Investigator should follow the procedures for reporting an SAE.

9.5 Expedited Reporting

The Sponsor/designee will report all relevant information about SUSARs that are fatal or life-threatening as soon as possible to the relevant authorities in all the countries concerned, and in any case no later than 7 days after knowledge by the Sponsor/designee of such a case.

All other SUSARs (except fatal/life-threatening) will be reported to the relevant authorities as soon as possible but within a maximum of 15 days of first knowledge by the Sponsor/designee.

When an event is considered to be a SUSAR, the blind will be broken by [REDACTED] for that specific patient. The blind will be maintained for persons responsible for the ongoing conduct of the study.

The Sponsor/designee will also report any additional expedited safety reports required in accordance with the timelines outlined in country-specific legislation.

The Sponsor/designee will also inform all investigators as required per local regulation.

The requirements above refer to the requirements relating to the investigational medicinal product.

Expedited reporting of SUSARs related to non-investigational medical products (NIMPs) is not required. All SARs, regardless of expectedness, will be reported to the manufacturer of the marketed product. Line listings of cases related to NIMPs will be included in the Development Safety Update Report.

9.6 Special Situation Reports

Special situation reports include reports of overdose, misuse, abuse, medication error, and reports of adverse reactions associated with product complaints.

- **Overdose:** Refers to the administration of a quantity of a medicinal product given per administration or cumulatively (accidentally or intentionally), which is above the maximum recommended dose according to the protocol. Clinical judgment should always be applied. In cases of a discrepancy in the drug accountability, an overdose will be established only when it is clear that the patient has taken additional dose(s) or the Investigator has reason to suspect that the patient has taken additional dose(s).
- **Misuse:** Refers to situations where the medicinal product is intentionally and inappropriately used in a way that is not in accordance with the protocol instructions or local prescribing information and may be accompanied by harmful physical and/or psychological effects.
- **Abuse:** Is defined as persistent or sporadic, intentional excessive use of a medicinal product, which is accompanied by harmful physical or psychological effects.
- **Medication error:** Is any unintentional error in the prescribing, dispensing, or administration of a medicinal product by a healthcare professional, patient, or consumer, respectively. The administration or consumption of the unassigned treatment and administration of an expired product are always reportable as medication errors, cases of patients missing doses of the investigational product are not considered reportable as medication error.

- **Product complaint:** Is defined as any written, electronic, or oral communication that alleges deficiencies related to the identity, quality, durability, reliability, safety, effectiveness, or performance of a drug or device after it is released for distribution. A special situations report form will only be completed if a complaint is associated with an ADR.

All special situation events as described above must be reported on the special situations report form and faxed/mailed to [REDACTED] (contact information listed below) within 24 hours of knowledge of the event. All adverse events associated with these Special Situation reports should be reported as adverse events or SAEs as well as recorded on the adverse event eCRF and/or the SAE report form. Details of the symptoms and signs, clinical management, and outcome should be provided, when available.

